This is intended to be a prospective study. Patients will contact the PI for a standard clinical evaluation, which includes palpation of the first extensor compartment and application of the Finkelstein test.² Those diagnosed with de Quervain's disease and who fit all inclusion criteria will receive a detailed verbal description of the study from one of the doctors, who will then attain written, informed consent from willing participants. The PI will then administer either a blind or US-guided injection. The patient will return for follow-up appointments at 6-8 weeks and 12-16 weeks and will undergo another physical exam to determine pain relief. A phone call follow-up will also be placed one year after the injection in order to determine long-term effectiveness. Once 20 study subjects in each group (40 total) have been enrolled and completed treatment, the data will undergo statistical analysis.

This study poses minimal or no physical risk to study subjects, as the US-guided injection should show better accuracy and pain relief for patients than the current standard treatment (blind injection).

All Injections will consist of 6 mg betamethasone and 4 cc 1% lidocaine without epinephrine, which is standard of care treatment.

In summary, we aim to perform a prospective study to evaluate the effectiveness of blind corticosteroid injections to US-guided injections for the treatment of de Quervain's disease. The results of the study will be used to validate current injection protocols or support the incorporation of ultrasonography to treat the disease.

Risk to Subjects:

A minimal physical risk is temporary inflammation around the wrist which accompanies any steroid injection. There is no risk involved with the addition of ultrasound. There is a slight risk of loss of confidentiality.

Data Analysis:

The mean DASH scores from the control group (blind injection) and the treatment group (US-guided injection) will be compared with a t-test to discern any significant statistical difference.

Plan for evaluating problems and adverse events (AEs):

The PI will address any unforeseen problems or events related to the study and the study coordinator will report promptly to the IRB.

References:

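### Local effects of the injection are neither systematically recorded nor tabulated by group, so a conclusion favouring ultrasound would have no planned harm data by technique

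*Combined protocol and SAP*

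**What the plan says.** All of the relevant text is in the combined protocol and SAP.

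- **Plan for evaluating problems and adverse events (AEs)** is one sentence: "The PI will address any unforeseen problems or events related to the study", with prompt reporting to the IRB by the study coordinator.
- **Risk to Subjects** names one physical harm: "A minimal physical risk is temporary inflammation around the wrist which accompanies any steroid injection". It adds: "There is no risk involved with the addition of ultrasound".
- **Study Design** gives the purpose of the contacts. At 6-8 and 12-16 weeks the patient "will undergo another physical exam to determine pain relief". For the last contact: "A phone call follow-up will also be placed one year after the injection in order to determine long-term effectiveness".
- **Study Design** also gives a reason for regarding the study as low risk: "This study poses minimal or no physical risk to study subjects, as the US-guided injection should show better accuracy". The sentence goes on to cite better pain relief as well.
- **Data Analysis** has one comparison: the mean DASH scores of the two groups "will be compared with a t-test to discern any significant statistical difference".
- **Study Design** ends by saying that the results will be used either to confirm present injection practice or to back the adoption of ultrasound.

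**The concern.** The study is meant to inform a choice between two ways of giving the same injection. Such a choice normally weighs benefit against harm. Here the benefit side has an outcome and a test, and the harm side has neither.

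The adverse-event sentence does not fill the gap. It says who deals with problems and who tells the IRB, and on its natural reading it is limited to what was not foreseen. The only physical harm that the protocol names is foreseen by the protocol's own account.

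If the DASH result favoured ultrasound, the report could offer no planned data on local effects by technique. A statement that no unforeseen events occurred could then be misread as a finding of no harm. Harm data that were not collected cannot be recovered at the analysis stage.

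**Working it through.** **1. The plan's own figure.** Study Design gives 20 patients per group and 40 in total; 20 + 20 = 40, which agrees. No alpha, power, effect size or SD is given, so the number itself cannot be re-derived. The point does not depend on that.

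**2. Where could local effects be recorded or compared?** Each candidate place in the text:

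| Place | What it provides for | Local effects recorded for every patient? | Compared by group? |
|---|---|---|---|
| AE plan | Handling of unforeseen problems or events; IRB reporting | Not specified | Not specified |
| Risk to Subjects | Names temporary inflammation; asserts no added risk from ultrasound | Not specified | Not specified |
| 6-8 and 12-16 week visits | Physical exam for pain relief | Not specified | Not specified |
| One-year call | Long-term effectiveness | Not specified | Not specified |
| Data Analysis | t-test of mean DASH | Not applicable | DASH only |

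The gap has three sources: the scope of the AE sentence, contacts described for efficacy only, and an analysis limited to DASH. Removing the word *unforeseen* would not by itself create a comparison.

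**3. What could 20 per group show if the data were collected?** The documents give no event rates, so the rates below are assumptions.

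*Upper bound after 0 events in 20.* One-sided 95%: 1 − 0.05^(1/20) = 1 − 0.861 = 13.9%. Upper limit of the two-sided 95% exact interval: 1 − 0.025^(1/20) = 1 − 0.832 = 16.8%.

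*Chance of at least one event in a group,* 1 − (1 − p)^20:
- p = 5%: 1 − 0.358 = 64%
- p = 10%: 1 − 0.122 = 88%
- p = 20%: 1 − 0.012 = 99%

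*Approximate 95% half-width for a difference,* 1.96 × √(2p(1 − p)/20), at a common rate p:
- p = 10%: 1.96 × √0.009 = 19 points
- p = 20%: 1.96 × √0.016 = 25 points
- p = 30%: 1.96 × √0.021 = 28 points

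*Power at two-sided 0.05.* The Fisher figures sum the probabilities of all significant tables with 20 per group.

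| Assumed rates | Normal approximation | Fisher exact |
|---|---|---|
| 20% vs 5% | 29% | 17% |
| 30% vs 10% | 35% | 24% |
| 40% vs 10% | 60% | 49% |
| 50% vs 10% | 81% | 74% |

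Effects that are not rare would probably be seen. Only a very large difference between groups could be detected formally.

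**The case against.** The strongest reply has four parts.

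- **The AE sentence is a reporting rule, and its scope is ambiguous.** *Unforeseen* may qualify only the problems, so that every study-related event is covered. That reading is possible. Even so, handling events and reporting them to the IRB is not systematic recording, and it yields no table by group.
- **Capture is not ruled out.** A reader might infer that local effects will be captured for none of the 40 patients, or that the trial can say nothing at all about local harm. The documents do not support that: each patient is examined twice, and a persisting problem could be seen and noted. What stands is that no systematic capture is specified.
- **There is little ground to expect a difference.** A reader might infer that needle placement is all that separates the groups, and that several known harms depend on it. The documents support neither. They name one local effect and describe it as common to any steroid injection. Background links accuracy of placement to pain relief, not to harm. No randomisation is described, so the groups may also differ in their patients. This limits what a table could show, but it does not justify planning none.
- **The data would be weak.** The named effect is temporary and the first contact is at 6-8 weeks, so patients would be recalling it. At 20 per group, power is low. Both points are right. They argue for a light method and cautious wording. With no plan, even descriptive data may not exist.

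A reader might also treat the sentence that rests low risk on the expected superiority of ultrasound as a safety failure in itself. It is circular, since it uses the study hypothesis as its reason, and it should not be cited as evidence of safety. But the low-risk claim also has Risk to Subjects and the standard-of-care statement behind it, so this is a secondary point of wording.

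**Conclusion.** The point holds as a gap in the plan. No section specifies systematic recording of local effects or a tabulation by group, and on the natural reading the one named harm lies outside the AE sentence. A conclusion supporting ultrasound would therefore rest on DASH, with no planned harm data by technique.

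The gain from closing the gap is modest. The table would describe local effects and would not test safety: with no events in a group, a true rate of up to about 14% would remain compatible with the data. A lack of difference must not be read as equal safety, and a difference could not be attributed to technique alone. The textual finding needs no assumed figure. The power and half-width results rest on the assumed event rates shown.

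**What to change.** 1. **AE section.** At the 6-8 week visit, the 12-16 week visit and the one-year call, ask every patient in both groups the same short set of questions on local effects since the injection, and record the answers whether or not the effect was foreseen. Inflammation or flare belongs on the list because the protocol names inflammation. Any further item is an assumption for the sponsor to confirm. Keep the IRB reporting sentence as a separate matter.
2. **Data Analysis.** Add one descriptive table: the number and proportion of patients with each local effect, by group, with exact confidence intervals. State that it is descriptive, that absence of a difference does not show equal safety, and that the groups are not described as randomised.
3. **Wording.** In Study Design, do not use the expected superiority of ultrasound as the reason for low risk.

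The cost is a short question set at contacts already planned, one table and a minor amendment. The drawback is that early, transient effects would be reported from memory at 6-8 weeks, and the report should say so.
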